7.3 Demographic and baseline variables

The baseline patients’ eligibility and characteristics of the mITT population will be described and will be presented in a summary table. This table will be structured with a column for each treatment group and a column for the total population in the order (DTG/RPV, control, and Total population). This summary table will be annotated with the total population size for each treatment group and the total population. The following variables will be described at baseline: Age, gender, ethnic, transmission group, child bearing potential, year of HIV diagnosis, Known duration since HIV diagnosis, duration of ART therapy, Positive Hep B antigen, Positive Hep C antibody, CD4 and CD8 cell count, CD4/CD8 ratio, antiretroviral treatment at baseline, NRT-backbone, PI received at baseline, body mass index, alcohol intake, smoking, recreational drug use, diabetes, metabolic parameters (LDL-c, HDL-c, total cholesterol (TC), triglycerides and TC/HDL ratio), glucose, total protein, hsCRP, Creatinine clearance (e-GFR), presence of M184V mutation, number of PI mutation, number of NRTI mutation and number of allowed NNRTI mutation. The summary statistics will be produced in accordance with section 7.

7.4 Concurrent Illnesses and Medical Conditions

The frequency of comorbidities will be described at baseline. The summary statistics will be produced in accordance with section 7.

7.5 Prior and Concurrent Medications

All medications ongoing at the start of the treatment or started during the study treatment will be described. The summary statistics will be produced in accordance with section 7.

7.6 Treatment Compliance

Adherence during the trial will be monitored by subject questioning regarding missed tablets at each visit. Compliance rate for each participant will be estimated by the number of pills consumed divided by the number of pills that will be theoretically consumed and will be classified as low (<80%), medium (80-95%), and high (95-100%). The summary statistics will be produced in accordance with section 7. Generalised Estimating Equation (GEE) model will be used to compare the proportion of participants

with compliance rate <95% (not classified as high) between the 2 treatment groups over time with unstructured covariance matrix. This analysis will be performed if more than 20% of participants are not classified as high. The model will include treatment group, time and interaction between treatment group and time. Time will be considered as a categorical variable (0, 12, 24, 48, 60, 72, and 96 weeks) according to the planned visits. The proportion of participants with compliance rate <95% will be done at each visit.

8. Efficacy Analyses

8.1 Primary Efficacy Analysis

Virologic outcome will be determined by the last available measurement while the participant is on treatment and continued on trial within the time window (see Table A, section 6.2).

The primary efficacy analysis will be performed at week 48 with the mITT population. The proportion of patients with treatment success will be estimated by the number of patients with HIV-RNA<50 copies/mL up to week 48 with no discontinuation of the study or the study treatment at week 48 divided by the total number of participants in the mITT population. The associated two-sided 95% confidence interval will be calculated for each treatment group. We will also calculate the difference in treatment efficacy between the two treatment groups by measuring the difference in the percentage of participants with therapeutic success (i.e., DTG/RPV success rate minus the control success rate). The two-sided 95% confidence interval of the difference in therapeutic success rate will be given by the following formula (A):

$$(\hat{p}_1 - \hat{p}_2) \pm 1.96 \sqrt{\frac{\hat{p}_1 \hat{q}_1}{n_1} + \frac{\hat{p}_2 \hat{q}_2}{n_2}} \quad \text{where } \hat{q} = 1 - \hat{p}$$

The effect of study treatment will also be assessed in the mITT population using logistic regression model with treatment group adjusted for the presence of M184V mutation at baseline and CD4 count at baseline (above versus below 350 cells/ μ L) as well as all baseline variables potentially associated with the outcome, with univariable P-value <0.10 as described above in the section 6.4.2.

Sensitivity analyses will be performed with both the per-protocol and the switch included populations.

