7 TRIAL MEDICATION

7.1 Name and description of investigational medicinal product(s)

Subjects will discontinue their usual boosted protease inhibitor or other ARV regimen (including Anatomical Therapeutic Chemical Classification System codes: JO5AB, JO5AE, JO5AF, JO5AG, JO5AR, JO5AX) and will switch to DTG plus RPV at baseline or week 48.

ViiV will supply Dolutegravir 50mg / Rilpivirine 25mg FDC tablets in the form of “Juluca” (which will be labelled in accordance with annex 13 requirements).

From baseline to week 96 or from week 48 to week 96, as randomised, participants will take a DTG/ RPV combined tablet once a day orally. Participants in the deferred group will continue to take their usual ARV regimen from baseline to week 48 until they switch to DTG/ RPV combined tablet.

The early switch group will be dispensed a supply of DTG/RPV combined tablets at baseline, week 4, 12 and 24. Both the early switch group and deferred switch group will be dispensed supply of DTG/RPV combined tablets at week 48, 52 and 72. Please refer to the study specific pharmacy manual for more information. Note, dispensing weeks may be modified with sponsor’s approval and in line with local regulations (if required). Prior to switch subjects will continue to be dispensed standard care boosted protease inhibitor or other ARV regimen.

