3.1 Study Objectives

The primary objective of this trial is to compare viral load outcomes on DTG/RPV FDC regimen (experimental arm) to continued ART regimen (control arm) at 48 weeks as measured by HIV-1 RNA below or confirmed ≥ 50 copies/mL.

Secondary objectives are:

- (a) To investigate whether switching patients to DTG/RPV FDC is associated with improvement of lipid profile, patient satisfaction, quality of life and potential for drug-drug interactions, investigated over time through 96 weeks with evaluation (and comparison to control arm) at week 24, 48 and 96.
- (b) To evaluate DTG and RPV trough concentrations
- (c) Changes in cell associated virus (using Peripheral Blood Monoclonal Cell (PBMC) analysis)

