3.2 Study endpoints

3.2.1 Primary endpoint/outcome

The primary endpoint is the proportion of participants free of therapeutic failure at week 48 (HIV RNA <50 copies/mL and no discontinuation). Therapeutic failure is defined as virologic failure or discontinuation with HIV RNA <50 copies/mL. Discontinuation is defined by the study follow-up stop or any change or modification in the study treatment regimen.

The following procedure will be used to classify the participants.

1. Virological failure:

- (a) Any patient with HIV RNA levels ≥ 50 copies/mL at any time points will have a repeat test on a second measurement within 2 weeks apart. If the result from the second measurement is <50 copies/mL, the patient will be categorized as HIV-RNA <50 copies/mL. If the result from the second measurement is ≥ 50 copies/mL, the patient will be categorized as virological failure.
- (b) If a patient has HIV-RNA ≥ 50 copies/mL at a given time point and stops the study or at least one drug from the study treatment combination for any reason, he or she will be categorized as virological failure.
- (c) If a patient discontinues the study or at least one drug from the study treatment combination at a given time point because of lack of efficacy then the patient will be categorized as virological failure.

2. Discontinuation (no virological data)

All discontinuations with HIV RNA <50 copies/mL will be considered as no virological data. There are three main reasons for no data at analysis time point:

- (a) Discontinuation due to Adverse Event (AE) or Death.

Any patient who discontinues the study or the study treatment with HIV-RNA is < 50 copies/mL because of AE or death will be classified as discontinuation due to AE or death at from the date of discontinuation.

(b) Discontinuation for Other Reasons.

If a patient discontinues the study follow-up or changes or modifies any drug in the study treatment when his or her HIV-1-RNA is < 50 copies/mL, he or she will be categorized as discontinued for other reasons at from the date of discontinuation.

(c) On study but missing data at analysis time point.

For example, if a participant has no data at analysis time point, but there is an HIV-RNA measurement after the analysis time point, this patient will be considered On Study but with Missing Data at analysis time point.

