4.1 General Study Design and Plan

This trial is an open-label, randomised, 2 arms, parallel-group, multicentre trial, comparing an immediate versus a deferred switch from a boosted PI containing regimen to a dual therapy with DTG and RPV in HIV infected patients with a history of virological failure with NNRTIs or baseline transmitted drug resistance and having developed a K103N mutation. The trial will be conducted within the NEAT ID network and include sites in 7 countries that have an excellent track record in clinical research. After screening, participants will be randomised 2:1 to switch to DTG/RPV at baseline or at 48 weeks.

The intervention will consist of immediate switch to DTG 50 mg OD + RPV 25 mg OD regimen at baseline or maintaining the current antiretroviral therapy for 48 weeks. At week 48, all participants in the deferred switch group with virological success will be switched to DTG 50 mg OD + RPV 25 mg OD therapy, and all participants will be followed for additional 48-weeks until week 96 (see figure).

After the screening visit, participants will be seen at baseline, weeks 4, 12, 24, 48, 52, 60, 72, 96, and either a follow-up visit (30 days (+/- 7 days) after week 96 visit) or an early termination visit. A week 60 visit may be an optional visit and performed for subjects on the control arm (3 months after therapeutic modification) as required per national guidelines. At each visit, participants will have routine investigations and will include viral load, CD4 & CD8, haematology (including haemoglobin, white cell count and differential, platelets), biochemistry (including sodium, potassium, creatinine, albumin, glucose, ALT, AST, ALP, total bilirubin, total cholesterol, HDL, LDL, triglycerides), PK, PBMC, quality of life questionnaires, patient satisfaction questionnaire, Pittsburgh sleep questionnaire, DDI assessment & urine sample (for haematuria, proteinuria, glycosuria, leukocytes) for full list of investigations please see section 4.4.

Statistical Analysis Plan

WISARD Study Protocol

Haematology Including:
 
 • Platelet count • RBC Count (indices MCV & MCH) • WBC count (absolute) • Haemoglobin • Hamatocrit RBC 
Count indices:
 
 • MCV • MCH 
Automated WBC differentials:
 
 • Neutrophils • Lymphocytes • Monocytes • Eosinophils • Basophils 	x	x	x	x	x	x	x	x	x	

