6.3.3 Switch Included Population

In addition, a “Switch Included” analysis will be conducted, to check the outcomes of participants who discontinued randomised treatment for any reason. This analysis will follow the same methods as FDA Snapshot, but will include HIV RNA data from all participants with results available at Week 48, whether they are on or off randomised treatment. There will be no formal non inferiority outcome analysis as this is a pilot study.

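### The week-48 window (days 295-378) contains the whole week-52 visit, and nothing closes it at the control arm's week-48 switch, so a control participant can be classified on a sample taken on DTG/RPV

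*SAP*

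**What the plan says.** SAP 8.1 fixes the sample for the primary outcome: "Virologic outcome will be determined by the last available measurement while the participant is on treatment and continued on trial within the time window". The windows are in SAP 6.2, in one table for both arms. Week 48 covers days 295 to 378, the next window (week 72) opens at day 463, and week 52 has no window of its own.

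Success in SAP 8.1 is HIV RNA below 50 copies/mL "up to week 48 with no discontinuation of the study or the study treatment at week 48". SAP 8.2 applies the same windows to the secondary efficacy outcomes.

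Week 52 (± 7 days) is a scheduled visit (protocol 6.8). Both arms attend it and have HIV RNA measured (protocol Appendix 1). Protocol 7.1 places the control switch at week 48: "Both the early switch group and deferred switch group will be dispensed supply of DTG/RPV combined tablets at week 48, 52 and 72". Protocol 7.5 agrees.

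The comparison intended is to "compare viral load outcomes on DTG/RPV FDC regimen (experimental arm) to continued ART regimen (control arm) at 48 weeks" (SAP 3.1), with control "maintaining the current antiretroviral therapy for 48 weeks" (SAP 4.1). SAP 3.2.1 adds: "Discontinuation is defined by the study follow-up stop or any change or modification in the study treatment regimen".

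**The concern.** The control condition is continued ART for 48 weeks, but the sample-selection rule runs about six weeks past the nominal switch date and takes the latest value it finds. After the switch a control participant is still on study medication and still on trial, so the two conditions in SAP 8.1 do not remove the week-52 sample. A programmer who follows SAP 8.1 and 6.2 as written would classify that participant on the experimental drug. This does not depend on a missed visit: when both samples exist, week 52 overrides week 48.

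At stake is whether the primary contrast, and the week-48 secondary outcomes at 50 and 200 copies/mL, measure what SAP 3.1 says they measure.

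**Working it through.** 1. **Reproduce the SAP window.** Weeks 42-54 give a lower limit of 42 × 7 + 1 = 295 and an upper limit of 54 × 7 = 378. The same rule reproduces all five rows of the SAP 6.2 table.

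2. **Place the visits (7 × week ± 7 days).**

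| Visit | Baseline = day 0 | Baseline = day 1 | Inside 295-378? |
|---|---|---|---|
| Week 48 | 329-343 | 330-344 | Yes |
| Week 52 | 357-371 | 358-372 | Yes, all 15 days |
| Week 60 (optional) | 413-427 | 414-428 | No |

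If week 52 is instead timed 28 ± 7 days from the actual week-48 visit, it falls on days 350-378 (351-379 with baseline as day 1). At most one extreme day then lies outside the window.

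3. **Gap from switch to week-52 sample.** Nominal 364 − 336 = 28 days; minimum 357 − 343 = 14; maximum 371 − 329 = 42.

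4. **Look for a text that closes the window for control.**
   - SAP 8.1, "up to week 48 with no discontinuation of the study or the study treatment at week 48": does not say whether week 48 means the visit or the window of that name.
   - SAP 6.3.3, Switch Included analysis, which "will include HIV RNA data from all participants with results available at Week 48, whether they are on or off randomised treatment": suggests that the primary analysis stays on randomised treatment, but deferred DTG/RPV is part of what control was randomised to.
   - SAP 3.1 and 4.1: describe 48 weeks of continued ART but set no sample cut-off.
   - SAP 3.2.1, "Discontinuation is defined by the study follow-up stop or any change or modification in the study treatment regimen": would close the window, but read literally it also makes the planned control switch a discontinuation, hence a therapeutic failure. That is plainly not intended.

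5. **Size, using SAP formula (A).** The difference is p1 − p2, with limits ± 1.96 × √(p1q1/n1 + p2q2/n2), n1 = 100 and n2 = 50. The formula reproduces the plan's lower limits of −7.4% (95% v 95%) and −9.3% (95% v 100%). Starting from the plan's own 95% v 96% row:

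| DTG/RPV | Control | Difference (points) | 95% CI |
|---|---|---|---|
| 95/100 | 48/50 (plan's row) | −1.0 | −7.9 to 5.9 |
| 95/100 | 47/50 (one control success becomes a failure) | +1.0 | −6.8 to 8.8 |
| 95/100 | 49/50 (one control failure becomes a success) | −3.0 | −8.8 to 2.8 |

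Each reclassified control participant moves the difference by 1/50 = 2 points. One can change the sign of the estimate, but all three intervals include zero. The one-participant shifts are illustrations, not forecasts.

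**The case against.** The strongest reply is that a pre-switch intent is clear enough. Besides the texts above, protocol 9.2.2 classifies outcomes at week 48 by discontinuation of randomised treatment, and protocol 6.19 ties virological failure to the assigned treatment. Together these make a post-switch control sample an unlikely reading. They support the intent, but none states a cut-off, and assigned treatment can include deferred DTG/RPV. SAP 8.1 also calls the window table Table A, a label not visible in the text reviewed. A caption or footnote there could settle the point, but none was found.

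The second reply is that few participants can be reclassified, and most of it stands:
- Whoever has the same class at both visits is unaffected.
- Under SAP 4.1 only control participants with virological success switch, so a known failure could not be rescued by a post-switch value. Protocol 7.1 and 7.5 carry no such condition, so this protection depends on how those texts are reconciled.
- SAP 3.2.1 calls for a retest within 2 weeks, which would resolve many raised week-48 values before week 52. SAP 3.2.2(a) and protocol 6.19 require at least 2 weeks between measurements, so some could remain open.
- A single raised week-52 value is not a failure unless it is confirmed or followed by stopping.

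The third reply is that only control needs a cut-off, because DTG/RPV participants take the same regimen at weeks 48 and 52. That would cure the stated defect. It would also leave the DTG/RPV arm alone with a second chance at week 52, so a common limit is preferable.

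**Conclusion.** The concern holds and should be fixed. As written, the rule selects a week-52 sample for a switched control participant who has one, and that sample is taken on DTG/RPV. Other passages point to a different intent but do not override the rule.

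The effect is probably small, and its number and direction cannot be determined from the documents. Exposure is limited to unconfirmed week-48 values, week-48 samples lost at an attended visit, and new rebounds after the switch. It also needs a week-52 result at the data cut. The primary analysis is timed to the last week-48 visit (SAP 6.1), so the latest enrolled may have none. Confirmed failures still count under SAP 3.2.1. No week-48 margin is at risk: "There will be no formal non inferiority outcome analysis as this is a pilot study" (SAP 6.3.3). The 2 points per control participant assumes the planned 50 in that arm.

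**What to change.** In SAP 6.2 and 8.1, apply one rule to both arms: use the last in-window HIV RNA up to and including the participant's week-48 visit; week-52 visit samples are not eligible. For control, also require the sample to be on or before the first DTG/RPV dose. Visit samples are already drawn pre-dose (protocol 6.8), so a control week-48 visit sample qualifies. A late week-48 visit, for example on day 360, counts in either arm.

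Apply the same rule to the week-48 outcomes at 50 and 200 copies/mL. State in SAP 3.2.1 that the planned control switch is not a discontinuation. Handle retests of a raised week-48 value under the confirmation rule, outside the window limit. Flag control retests taken after the switch, and add a sensitivity analysis that counts the unconfirmed value as failure.

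The cost is wording in SAP 3.2.1, 6.2, 8.1 and 8.2. No new data are needed, since visit dates and study-medication start dates are already recorded (protocol 10.1.2). The downside is that a participant with no in-window sample up to the week-48 visit can no longer be rescued by week 52 and may count as missing, hence failure (SAP 6.5). From the same starting row, one such loss in DTG/RPV costs 1 point (94/100 v 48/50: −2.0, CI −9.2 to 5.2). One in control costs that arm 2 points (95/100 v 47/50: +1.0, CI −6.8 to 8.8).

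Two related inconsistencies need separate reconciliation: the retest interval and threshold (SAP 3.2.1 against SAP 3.2.2(a) and protocol 6.19), and which control participants switch (SAP 4.1 against protocol 7.1 and 7.5).

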9.2.2 Primary outcome analysis

The primary endpoint will be a comparison of the percentage of participants with undetectable plasma HIV RNA levels at Week 48.

Undetectable will be defined as plasma RNA levels of <50 copies/ML. Participants with missing data at analysis time points will be considered as having lost undetectable plasma HIV-1 RNA levels. Any patient with HIV RNA levels >50 copies/ML at analysis time points will have a repeat test (see section 6.18 for repeat testing process). If the result from the repeat test is below 50 copies/ML, the patient will be classified as a responder. This is to prevent false positive HIV RNA results being classified as treatment failures.

The analysis will be performed using the FDA Snapshot method. The primary population for analysis will be Intent to Treat, including all randomised patients who have received at least one dose of study medication.

Participants will be categorised as follows, based on their HIV RNA results and disposition up to the end of the trial.

HIV RNA <50 copies/ML at Week 48

HIV RNA confirmed >50 copies/ML at Week 48 (virological failure)

Missing HIV RNA data – discontinued randomised treatment for adverse events

Missing HIV RNA data – discontinued randomised treatment for other reasons

The intention of this study is to be a comparative pilot study. All analysis details will be included in Statistical Analysis Plan.

CONFIDENTIAL

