9.4 Adjusted analysis

The primary efficacy analysis will be by multiple logistic regression. This analysis will be adjusted for two baseline categorical variables which might influence the 48-week outcome: presence of M184V mutation at baseline and CD4 count at baseline (above versus below 350 cells/UI).

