6.4.2 Adjusted analysis

The treatment effect will also be assessed adjusted for baseline variables which might influence the 48-week outcome.

Factors associated with the outcome will be tested using univariable logistic regression models. The following baseline variables will be tested: Age, gender, ethnic (black vs white), transmission group (MSM vs Other), Known duration since HIV diagnosis, duration of ART therapy, Positive Hep B antigen (yes vs no), Positive Hep C antibody (yes vs no), CD4 (above versus below 350 cells/ μ L), CD4/CD8 ratio, NRTI-backbone, PI received at baseline (yes vs no), body mass index, alcohol intake (yes vs no), current smoking (yes vs no), recreational drug use (yes vs no), diabetes (yes vs no), metabolic parameters (LDL-c, HDL-c, total cholesterol (TC), triglycerides and TC/HDL ratio), glucose, total protein, hsCRP, Creatinine clearance (e-GFR), presence of M184V mutation at baseline (yes vs no), number of PI mutation, number of NRTI mutation and number of allowed NNRTI mutation. Continuous variables will be modelled as continuous or as tertiles based on the AIC of the corresponding univariable model. Variables with univariable p-value <0.10 will be retained for the multivariable analysis.

All potential confounders that are known in the literature will also be included, such as the presence of M184V mutation at baseline and CD4 count at baseline (above versus below 350 cells/ μ L).

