Genotypic resistance testing will be performed in participants with confirmed pVL >50 copies/mL and compared to previous resistance tests. Resistance interpretation will be given by using the Stanford algorithm (<https://hivdb.stanford.edu/hivdb/by-mutations>). The incidence of new resistance mutations will be described and compared between the two treatment groups. The frequency of new mutations conferring resistance to any antiretroviral drug will be given. A table will be built listing all participants with drug resistance mutations by treatment group. The table will include the following information: Patient Id, ARV treatment at baseline, age, sex, CD4 nadir, CD4 count at baseline, CD4/CD8 ratio at baseline, ARV treatment at failure, 1st VL at failure, 2nd VL at failure, resistance mutation at baseline, resistance mutation at failure, drugs resistant at baseline, drugs resistant at failure, drugs concentration at failure.

(c) Proportion of participants with plasma HIV RNA <50 copies/mL at week 24, 48 and 96.

The proportion of participants with plasma HIV RNA <50 copies/mL will be defined as the proportion of participants with HIV RNA <50 copies/mL and no discontinuation of the study or the study treatment. It will be estimated by the number of patients with HIV-RNA<50 copies/mL and no discontinuation at the analysis time point divided by the total number of patients in the mITT population. The associated two-sided 95% exact (Clopper–Pearson) confidence intervals will be calculated for each group as well as the two-sided 95% confidence interval of the difference in the proportion between the two treatment groups. The confidence intervals for the difference in proportions will be calculated with formula (A) defined above. Discontinuation is defined by the discontinuation of the study or any change or modification in the study treatment.

(d) Proportion of participants with plasma HIV RNA <200 copies/mL at week 24, 48 and 96.

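### The simple Wald interval fixed for the week-48 difference is unreliable near 95% success with 100 and 50 participants, and one limit in the planning table is not what its formula gives

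*SAP*

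**What the plan says.** For the primary endpoint, SAP 8.1 first asks for the success proportion in each arm: "The associated two-sided 95% confidence interval will be calculated for each treatment group". No method is named for that interval. It then turns to the difference: "The two-sided 95% confidence interval of the difference in therapeutic success rate will be given by the following formula (A"), which is the difference plus or minus 1.96 times the square root of the sum of p(1-p)/n over the two arms. No alternative is given for sparse or empty cells.

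The planning table in Protocol 9.1 and SAP 5 takes 95% success in 100 DTG/RPV participants against 95% to 100% in 50 controls. Its last row (95% versus 100%) prints -9.3% to -0.1%.

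For the secondary proportions, SAP 8.2.1(c) says "The associated two-sided 95% exact (Clopper–Pearson) confidence intervals will be calculated for each group" and uses formula (A) for the difference. SAP 8.2.1(d) instead attaches Clopper-Pearson to the difference, and then also assigns formula (A) to it.

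SAP 8.1 adds a logistic model with M184V and baseline CD4, "as well as all baseline variables potentially associated with the outcome, with univariable P-value <0.10". SAP 6.4.2 presents this as additional ("The treatment effect will also be assessed adjusted for baseline variables") and sets the selection rule: "Variables with univariable p-value <0.10 will be retained for the multivariable analysis". Protocol 9.4, however, says "The primary efficacy analysis will be by multiple logistic regression", whereas Protocol 9.2.2 says "The primary endpoint will be a comparison of the percentage of participants with undetectable plasma HIV RNA levels at Week 48".

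**The concern.** The Wald interval estimates each arm's variance from its observed proportion. If an arm has no failures, its term is zero and the interval treats that arm's rate as known exactly. Yet 50 successes in 50 has an exact 95% lower limit of 92.9%. The plan tabulates this very case.

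Comparing the arms at week 48 is the stated primary objective, and with no formal test planned, readers will judge the comparison by this interval. An upper limit that falls below zero too often presents the new regimen as worse when it is not.

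Two lesser problems sit alongside. The documents do not agree on which analysis is primary, and the adjusted model screens many covariates against very few failures.

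**Working it through.** **Inputs.** n1 = 100 and n2 = 50; expected success 95%; control 95% to 100% (Protocol 9.1, SAP 5). Formula (A) from SAP 8.1. Loss to follow-up 15%, timing not stated (Protocol 6.12).

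**Planning table.** Formula (A) reproduces 11 of the 12 printed limits to one decimal. For the last row:

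- SE = sqrt(0.95 × 0.05/100 + 1 × 0/50) = 2.18 points
- 1.96 × SE = 4.27 points
- limits -5.0 ± 4.27 = -9.27% to -0.73%

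The printed upper limit is -0.1%. The printed pair is also asymmetric about -5.0% (half-widths 4.3 and 4.9), which formula (A) cannot produce. Continuity-corrected, pooled-variance, Newcombe, Agresti-Caffo and Miettinen-Nurminen intervals do not give -0.1% either.

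The same table by Miettinen-Nurminen, using the plan's fractional control counts:

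| Control | Formula (A) | Miettinen-Nurminen |
|---|---|---|
| 95% | -7.4, +7.4 | -7.2, +10.3 |
| 96% | -7.9, +5.9 | -8.0, +8.9 |
| 97% | -8.4, +4.4 | -8.8, +7.5 |
| 98% | -8.8, +2.8 | -9.6, +5.9 |
| 99% | -9.1, +1.1 | -10.4, +4.2 |
| 100% | -9.3, -0.7 | -11.2, +2.3 |

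**Chance of no control failure.** 0.95^50 = 7.7%; 0.98^50 = 36.4%.

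**Upper limit (%) when control is 50/50:**

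| DTG/RPV failures | Formula (A) | Miettinen-Nurminen | Newcombe |
|---|---|---|---|
| 3 | +0.34 | +4.25 | +4.40 |
| 4 | -0.16 | +3.28 | +3.54 |
| 7 | -2.00 | +0.35 | +0.98 |
| 8 | -2.68 | -0.63 | +0.13 |
| 9 | -3.39 | -1.61 | -0.72 |

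Formula (A) excludes zero from 4 failures, Miettinen-Nurminen from 8 and Newcombe from 9. Fisher's p is 0.30 for 96/100 versus 50/50, and 0.17 for 95/100 versus 50/50, the plan's own last row.

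**Exact coverage** (both binomials enumerated, DTG/RPV true rate 95%):

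| True control rate | Formula (A) | Miettinen-Nurminen |
|---|---|---|
| 95% | 92.0% | 96.1% |
| 96% | 93.3% | 95.6% |
| 97% | 95.4% | 97.4% |
| 98% | 94.9% | 97.4% |
| 99% | 94.4% | 97.0% |
| 99.5% | 95.2% | 98.1% |

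In the limiting case of a true 100% control rate, formula (A) covers 87.7%. At 95%/95% its upper limit is below zero in 7.0% of trials (nominal 2.5%), and 5.7 points of that come from trials with no control failure. The corresponding figures are 1.1% for Miettinen-Nurminen and 0.6% for Newcombe.

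**If all 15% loss counted as failure by week 48 (assumption).** Success of 85% in both arms gives formula (A) coverage of 94.0%; 0.95 × 0.85 = 80.75% in both gives 94.2%. Miettinen-Nurminen gives 94.9% in both cases.

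**Logistic model.** Expected failures are 100 × 0.05 = 5, plus 0 to 2.5 in control, so 5 to 7.5. With treatment, M184V and CD4 that is 5/3 = 1.7 to 7.5/3 = 2.5 failures per term. SAP 6.4.2 lists 30 variables, so 28 remain after M184V and CD4. One of these, positive hepatitis B antigen, is an exclusion criterion (Protocol 5.2), leaving 27. If each held its nominal 10% level, 27 × 0.10 = 2.7 would enter by chance. That leaves 5/5.7 = 0.9 to 7.5/5.7 = 1.3 failures per term. Under the 15%-loss assumption (22.5 to 28.9 failures) it is 3.9 to 5.1.

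**The case against.** The trial is a pilot, and SAP 6.3.3 rules out a formal non-inferiority analysis, so no week-48 decision depends on this interval. At the interim, SAP 6.6 sets the acceptance rule on the DTG/RPV arm's own interval and only explores the difference. Under-coverage is confined to near-equal rates around 95% to 96% and the limiting 100% case. Because discontinuation and missing data count as failure, a control arm without failures may be rarer than the planning rate suggests: 0.85^50 = 0.03% at 85%.

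The lower limit, which carries the risk of switching, is conservative under formula (A) near equality, missing in 1.0% of trials at 95%/95% and 1.4% at 95%/96%. Miettinen-Nurminen misses there in 2.9% and 3.5%, and Newcombe in 2.7% and 3.5%. The -0.1% entry changes neither a sign nor the quoted range of lower limits. SAP 8.2.1(c) already gives a per-arm method for nearly the same week-48 quantity. The logistic model is supplementary in the SAP, and a constant hepatitis B term would simply drop out.

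All of this stands and limits the severity. It does not justify pre-specifying an interval that misleads in a case the plan tabulates. The lower-limit trade-off is real but small, and it reverses against formula (A) at a 99% control rate (3.9% versus 2.8% for Newcombe). The 2.7 chance entries assume that the univariable tests hold their level with so few events, which has not been shown.

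**Conclusion.** The point holds and should be corrected. At the planning rate of 95% in both arms, formula (A) covers 92.0% and places DTG/RPV below control in 7.0% of trials, nearly three times the nominal 2.5%. In the plan's 95% versus 100% row it excludes zero, while Miettinen-Nurminen gives -11.2% to +2.3%. The size rests on success near 95% and on the planned arm sizes; it shrinks to about one point of coverage if success is nearer 81% to 85%.

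The -0.1% entry is an isolated error in both documents. The Clopper-Pearson wording in SAP 8.2.1(d) applies a one-sample method to a difference. The covariate screen and the conflict over the primary analysis are real but secondary. SAP 8.1 gives the per-arm proportions first, then the difference, then the logistic model, so Protocol 9.4 is the text out of line.

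**What to change.** - **SAP 8.1:** name Clopper-Pearson for each arm and the Miettinen-Nurminen score interval for the difference (DTG/RPV minus control), and state that this difference is the primary comparison. Newcombe's interval would also be acceptable.
- **SAP 8.2.1(c) and (d):** use the same interval for the difference; in (d), attach Clopper-Pearson to each arm. Name the same interval in SAP 6.6 for consistency.
- **SAP 6.4.2 and 8.1:** delete the p<0.10 screen. Keep one supportive logistic model with treatment, M184V and baseline CD4, fitted with a penalised likelihood such as Firth's because events are sparse.
- **Protocol 9.4:** describe the logistic model as supportive and the risk difference as primary.
- **Protocol 9.1 and SAP 5:** recompute the table (lower limits -11.2% to -7.2%, last upper limit +2.3%), or at least change -0.1% to -0.7%.

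The cost is wording and standard software options, with no new data. The planned worst-case lower limit becomes less favourable (-11.2% instead of -9.3%), and the lower limit misses slightly above its nominal 2.5% at near-equal rates.
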